9.9.3 Healthcare Utilization

Healthcare utilization (HCU) information data will be collected and classified according to the below definitions.

Details on how HCU will be confirmed can be found in each specific DEFINE AFib study addendum.

Table 6: Healthcare Utilization Definitions

Healthcare Utilizations (HCU)	All inpatient hospitalizations, outpatient hospital encounters, emergency department visits, clinic visits, urgent care visits, rehab center or other care location interactions (including remote visits)
CV-related HCU	A healthcare utilization relating to the heart and the blood vessels or the circulation (e.g., atrial fibrillation, myocardial infarction, stroke, peripheral vascular disease, heart failure).
AF-related HCU	HCU related to AF, suspected AF, AF treatment, or complications related to AF (including bleeding and drug toxicity as determined by treating clinician.
HF-related HCU	A healthcare utilization related to worsening heart failure signs and symptoms (as determined by treating clinicians) such as (but not limited to) hypervolemic and hypovolemic status requiring the administration, alteration, adjustment, or augmentation of HF therapy (diuretics, inotropes and/or vasodilators etc.) or the utilization of ultrafiltration devices.
Hospitalization	A therapeutic inpatient hospitalization (excludes outpatient and emergency room visits) lasting greater than or equal to 24 hours.
Non-hemorrhagic stroke	Rapid onset of a focal or global neurological deficit or other neurological signs/symptoms consistent with stroke; whereas focal, global cerebral or spinal dysfunction was NOT caused by a non-traumatic intraparenchymal, intraventricular, or subarachnoid hemorrhage, as determined by the treating clinician.
Systemic embolism	An embolus resulting in clinical and objective evidence of sudden loss of end organ perfusion.
TIA	New focal neurological deficit with rapid symptom resolution (usually 1 – 2 hours), always within 24 hours without tissue injury (based on neuroimaging) as determined by the treating clinician.

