4.1 Objectives

4.1.1 Primary Objective(s)

To evaluate whether summary and episodic measurements collected by market-released LINQ ICMs are able to predict increased AF-related healthcare utilization (HCU)

Endpoint: Confirmed healthcare visit in the inpatient hospital, outpatient hospital, clinic/office, emergency department, or other care location (including remote visits) where AF was a reason or suspected reason for healthcare interaction

DEFINE AFib Clinical Investigation Plan Medtronic Page 14 of 48 Version 4.0 (29JUL2022)

Version 4.0 (29JUL2022)

Page 15 of 48

5. Study Design

DEFINE AFib is a prospective, observational, post-market clinical study. This study will enroll approximately 5,000 patients (see section 13.1) in the United States who have a Reveal LINQ or LINQ II (or any other market-released LINQ device) and using an Apple iPhone®.

This study will utilize the Reveal LINQ and LINQ II ICM or newer commercial ICM models and a Medtronic, Inc. developed research application for the Apple, Inc. iPhone®. The research application will allow for the remote enrollment and follow-up of patients by first administering electronic consent, providing patients the option to share their data from the Apple Health app, Electronic Health Records through the Apple Health app or location data, and deploying scheduled and triggered surveys to collect patient reported outcome measures. The market-released LINQ device will collect and report standard cardiac parameters through the CareLink network. The purpose of this study is to evaluate whether summary and episodic measurements collected by the market-released LINQ ICM are able to predict increased AF-related healthcare utilization (HCU) in patients with device-detected AF.

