5.1 Healthcare Utilization Confirmation

Healthcare utilization and modification to treatment or management of AF will be reviewed and confirmed via EHR by healthcare site personnel for subjects with available health records to compare to patient completed surveys. Trained and Delegated personnel will be sent patient reported outcomes via a part 11 compliant system for only the subjects that are part of their care network or clinic and asked to confirm patient HCU reports. There will be a standardized set of questions related to each HCU and/or medication/treatment change that includes whether or not the patient-reported utilization/change truly occurred. The reason and specific details for each visit will be recorded (as determined by the treating clinician in the EHR). If there are errors in the patient report, the designated site personnel will have the opportunity to record a correction stating the true events that happened upon a patient's visit to their affiliated health care facility. This process will also be used for all exits performed by the sponsor, as outlined in section 9 of the DEFINE AFib Core CIP v3.0. Site personnel will be asked to determine patient's mortality status along with any HCUs or medication/treatment changes/certain clinical outcomes since the last reported event. Non-confirmable events will be noted as such and will not contribute to the study's endpoints.

Table 7 Healthcare Utilization Definitions

Healthcare Utilizations (HCU)	All inpatient hospitalizations, outpatient hospital encounters, emergency
	department visits, clinic visits, urgent care visits, rehab center or other care location
Otilizations (HCO)	interactions (including remote visits)

Version: 2.0 29JUL2022 Page 12 of 17

CV-related HCU	A healthcare utilization relating to the heart and the blood vessels or the circulation (e.g., atrial fibrillation, myocardial infarction, stroke, peripheral vascular disease, heart failure).
AF-related HCU	HCU related to AF, suspected AF, AF treatment, or complications related to AF (including bleeding and drug toxicity as determined by treating clinician.
HF-related HCU	A healthcare utilization related to worsening heart failure signs and symptoms (as determined by treating clinicians) such as (but not limited to) hypervolemic and hypovolemic status requiring the administration, alteration, adjustment, or augmentation of HF therapy (diuretics, inotropes and/or vasodilators etc.) or the utilization of ultrafiltration devices.

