4.1 Primary Objective

To evaluate whether summary and episodic measurements collected by market-released LINQ ICMs are able to predict increased AF-related healthcare utilization (HCU)

Endpoint: Confirmed healthcare visit in the inpatient hospital, outpatient hospital, clinic/office, emergency department, or other care location (including remote visits) where AF was a reason or suspected reason for healthcare interaction

[figure not shown]
Investigation Plan 5.

DEFINE AFib is an observational, post-market clinical study intended to leverage machine learning to evaluate the association between complex patterns of device-detected AF and elevated healthcare utilization, reduced QoL and specific clinical outcomes in patients with a LINQ ICM. These data will improve the business understanding of how data from the LINQ ICM can be used to guide the management of patients with AF.

This study is expected to be conducted at approximately 30 centers in the United States, and it will enroll approximately 5,000 patients (see section 13.1 of the CIP). Study subjects will be followed for up to 5 years, until study closure, or until their LINQ ICM either completes its service life or is explanted, upon which time they will no longer be followed. Study closure may occur when Medtronic requirements have been satisfied per the CIP and/or following a decision by Medtronic or applicable external parties (i.e. institutional review board (IRB) or regulatory authority) to discontinue the study.

Revision [2.0]

Page 7 of 25

Enrollment is anticipated to last for up to 3 years. The estimated total study duration is up to 7 years, representing a three-year enrollment period and up to 5 years of follow-up for all patients.

Inclusion Criteria

- Patients with a Reveal LINQ or LINQ II ICM who have a self-reported history of AF and who have received an ICM for the following device logged indications, categorized into the following groups:
 - o **Stroke**: Cryptogenic stroke indication
 - o **AF management**: AF management and post-ablation management indications
 - Suspected AF: Suspected AF and palpitations indications
- Individual access and ability to use an Apple iPhone® compatible with Medtronic's research app (iOS v. 13.X or higher)
- Patient is willing and able to comply with the protocol, including CareLink transmissions (requires
 adequate connectivity), remotely administered instructions, and remote survey participation
- Patient is 22 years of age or older

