7.9.1 Primary Objective

The primary objective require development of risk-prediction models for various endpoints using different data source combinations. This section describes a general framework that will be used to develop these models.

Prediction models

For each endpoint, two types of prediction modeling will be considered: one focusing on short term predictions and other on long term predictions. For both prediction modelling types, the following machine learning (ML)/artificial intelligence (AI) methods might be considered (but not limited to):

- Tree Boosting
- Temporal Convolutional networks feedforward neural network (TCN FFNN) (similar approach presented in Catling & Wolff (2020))

Dataset split

DEFINE AFib Statistical Analysis Plan Revision [2.0] Page 14 of 25 Medtronic

Predictive modelling requires the original data to be split into three smaller sets, one for training, one for validation and one for testing. The original data will be randomly split into those three datasets with 70%, 10% and 20% of patients in the training, validation, and testing datasets, respectively. A patient will only contribute data to one of the 3 datasets. To reduce impact of possible heterogeneity across sites, patients and LINQ model, randomization will be stratified by sites, LINQ indication, and LINQ model. Lastly, the testing dataset will only be used after the models under consideration have been trained and validated.

Data format

All predictive models will be trained using similar labeled examples. In particular, at a prediction time point **t** a patient **i** generates a labeled example (hereinafter referred as sliding window) which will be composed of the all features considered as relevant to the clinical endpoint (e.g. LINQ device data, EHR data, etc.) collected between **(t-b)** and **t**, and a binary label indicating if that patient had the clinical event of interest between time points **t+l** and **(t+l+w)**. Figure 1 illustrates the sliding window concept at time **t**. Notice a patient will provide multiple sliding windows.

[figure not shown]

Figure 1: A sliding window at time t is composed of all relevant features values observed from the most recent b days and a binary label indicating if event occurred between t+l and t+l+w. The rationale of the parameter l is to give leading time to the physicians to prevent an event for a patient with high risk of having that event between t+l and t+l+w

Data transformations

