All continuous variables will be centered and scaled. Categorical variables will be converted to into one-hot vectors.

Handling missing data

[figure not shown]
Due to the various types of data sources, handling missing data will depend on the requirements of the predictive model and on the data missing patterns observed in the training data. Thus, the decision on

DEFINE AFib Statistical Analysis Plan Form Medtronic Revision [2.0] Page 15 of 25

the methods to be used for handling missing data will be left to the discretion of the statistician/data scientist during the model development phase. However, this decision will be made prior of using the testing data.

Undersampling/Oversampling

Likely the training dataset will have many more instances (i.e. sliding windows) where a clinical event is not observed. Thus, random undersampling/oversampling methods might be needed to build the training dataset. Notice that these approaches will **not** be used to build the validation and test datasets.

DEFINE AFib Statistical Analysis Plan Form Medtronic Revision [2.0] Page 16 of 25

Training model

All models under consideration will be training with the goal of minimizing the cross-entropy loss function.

Tuning

Hyperparameters b, I and w will be determined via grid search algorithm using the validation set and the Area Under Receiver Operating Characteristic (AUROC) curve as the metric to be maximized. Finite set of reasonable values for b, I and w will be set during the exploratory data analysis.

The tuning approach for hyperparameters associated with the training model process (e.g. number of epochs, batch size, learning rate, optimizer, etc.) will be left to the discretion of the statistician/data scientist.

Testing

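### The primary endpoint does not separate planned from unplanned AF visits, so model performance cannot be read as prediction of increased or preventable utilization

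*Protocol*

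**What the plan says.** - **Objective.** SAP section 4.1 asks whether LINQ measurements "are able to predict increased AF-related healthcare utilization (HCU"). Protocol section 4.1.1 uses the same objective.
- **Endpoint.** Protocol section 4.1.1: "Confirmed healthcare visit in the inpatient hospital, outpatient hospital, clinic/office, emergency department, or other care location (including remote visits) where AF was a reason". Visits where AF was only suspected count too.
- **Definitions.** In Protocol section 9.9.3, Table 6, HCU covers "All inpatient hospitalizations, outpatient hospital encounters, emergency department visits, clinic visits, urgent care visits, rehab center or other care location interactions", remote visits included. AF-related HCU is "HCU related to AF, suspected AF, AF treatment, or complications related to AF". In the same table, HF-related HCU is limited to worsening heart failure. The AF definition has no such limit.
- **Label.** SAP section 7.9.1 gives each sliding window "a binary label indicating if that patient had the clinical event of interest between time points" that bound the prediction window. No baseline level or increase is defined.
- **Purpose of the lead time.** The Figure 1 caption in SAP section 7.9.1 states: "The rationale of the parameter l is to give leading time to the physicians to prevent an event".
- **Tuning.** The look-back b, lead time l and window width w "will be determined via grid search algorithm using the validation set", with AUROC as the quantity maximised.
- **What sites record.** Site Assisted Phase Addendum, section 5.1: "The reason and specific details for each visit will be recorded (as determined by the treating clinician in the EHR"). No rule for sorting visits into planned and unplanned appears in the visible text.

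**The concern.** Everyone enrolled reports a history of AF, and one of the three indication groups is AF management, including monitoring after ablation. Booked AF reviews and elective AF procedures are foreseeable in such a cohort. By its wording the endpoint counts each of them as a positive, with the same weight as an emergency visit for AF.

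A routine booked review is neither an increase in utilization nor an event that a warning could prevent. The label therefore mixes visits that the stated purpose is about with visits that it is not about. Tuning b, l and w on AUROC for this mixed label rewards whichever kind of visit is easiest to rank. The visible plan contains no analysis that would show which kind drove the result. What is at stake is the meaning of the headline figures: a good AUROC might not reflect warning of worsening AF, and a poor one might hide a real signal for unplanned visits.

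**Working it through.** **1. The plan's own figures (Protocol section 13.1, SAP section 6).**
- Patients with any HCU: 5,000 × 0.47 = 2,350. AF-related: 5,000 × 0.21 = 1,050. At 50% complete data: 1,175 and 525. All agree with the plan.
- Events for variable influence: 80/0.05/10 = 160 and 80/0.02/10 = 400. The algorithm range of 320 to 800 is twice these.
- The 21% works only with 5,000 patients as denominator, since 21% of 2,350 is 493.5. So 1,050 reads as patients with at least one AF-related HCU, although the sentence speaks of events.

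**2. Effect of mixing on AUROC.** AUROC is the probability that a random positive window scores above a random negative one. With p the planned share of positive windows and the same negatives throughout,

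AUROC(all) = p × AUROC(planned) + (1 − p) × AUROC(unplanned).

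The documents give neither p nor the class-specific values, so all inputs here are assumptions.

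| p | Planned 0.50, unplanned 0.75 | Planned 0.90, unplanned 0.50 |
|---|---|---|
| 0.2 | 0.70 | 0.58 |
| 0.4 | 0.65 | 0.66 |
| 0.6 | 0.60 | 0.74 |
| 0.8 | 0.55 | 0.82 |

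At p = 0.6: 0.6 × 0.50 + 0.4 × 0.75 = 0.60, and 0.6 × 0.90 + 0.4 × 0.50 = 0.74. On the SAP's descriptive scale the first is poor, although unplanned visits are predicted at 0.75. The second is good, although the model has no skill for unplanned visits. Sensitivity at a fixed threshold mixes in the same way, and overall PPV counts an alert followed only by a booked visit as correct.

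**3. Which direction is open.** Protocol section 13.3.1 names LINQ values as inputs, with medical history as an option. Planned visits unrelated to those values behave like the middle column (dilution). SAP section 7.9.1 also allows EHR data as features, and SAP section 5 lists procedures and clinical actions among the EHR data collected. If such features carry visit timing, the right-hand column (inflation) becomes possible.

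**4. Does the 21% fit the broad endpoint?** Assume each patient has planned AF visits at a constant rate (Poisson). The share with at least one in five years is 1 − exp(−5 × rate): 71%, 92% and 99% at 0.25, 0.5 and 1 per year. The plan's average follow-up is 5.2 million / 5,000 = 1,040 days, or 2.85 years, over which the shares are 51%, 76% and 94%. Against 21%, either planned AF visits are rare, or the retrospective count used a narrower definition or captured visits incompletely. The documents do not say.

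**5. Events left in the unplanned class.** Let u be the unplanned share (assumed), and suppose that the planning count covered all AF visits.

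| u | 1,050 × u (full data) | 525 × u (50% complete) | 20% test set at 50% complete |
|---|---|---|---|
| 0.8 | 840 | 420 | 84 |
| 0.6 | 630 | 315 | 63 |
| 0.4 | 420 | 210 | 42 |
| 0.2 | 210 | 105 | 21 |

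The 320 minimum is reached at 50% completeness only if u ≥ 320/525 = 0.61, and at full data if u ≥ 320/1,050 = 0.305.

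**The case against.** **AF treatment is genuine AF-related utilization.** An elective ablation booked because AF burden rose is arguably just what LINQ data should anticipate, and dropping such visits would discard legitimate events and could take the count below the plan's 320 minimum. This stands. It is a reason to keep the all-visit label and to give elective procedures their own class.

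**Part of the plan cannot be seen.** The standardised site questions and the HCU survey are not in the documents, and parts of Protocol section 13 and SAP section 7.9 are not shown. A planned/unplanned field or a narrower ancillary endpoint may exist. This stands as a caveat, but it does not alter the visible primary endpoint, label or test metrics.

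**Other safeguards exist.** SAP section 7.3 plans error analysis by cohort, section 7.9.1 plans a comparison with clinical practice, and section 7.8 allows revision after the interim analysis. None of these commits to a split by visit type.

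**Two stronger readings are tempting and are not supported.**
- A reader might infer that the model will largely learn appointment schedules. The documents list no appointment data as input and give no planned-visit share. Planned visits unrelated to device data would lower AUROC, not be learned.
- A reader might infer that planned visits will swamp the events planned for. If 30% of patients had four planned AF visits a year, 1,500 × 4 × 2.85 gives about 17,100 visits. But 1,050 reproduces as a count of patients, so the two cannot be compared. Counted as patients, a 10% share gives at most 500 and a 30% share at most 1,500, whatever the visit rate.

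Prevention is also the SAP's reason for the lead time and not part of the objective's wording. The gap between *increased* utilization and a yes/no visit label remains without it.

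**Conclusion.** The concern holds as a limit on interpretation. The visible primary endpoint pools scheduled, elective and unplanned AF visits, and *increased* utilization is never turned into a measurable quantity. The planned AUROC, sensitivity and PPV can support a statement about predicting any confirmed AF-related visit. They cannot support one about increased or preventable utilization.

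The size is unknown because the planned share is unknown. In the illustration with 60% of positive windows planned, the descriptive grade moves between poor (0.60) and good (0.74) in the direction opposite to the model's skill for unplanned visits. Those values rest wholly on assumed inputs, and the documents do not settle whether dilution or inflation would dominate. The point does not invalidate the study. It should be settled before the test set is used, because it decides what the primary result may be said to show.

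**What to change.** **Addendum section 5.1.** Have sites classify each confirmed AF-related HCU as scheduled follow-up, elective AF procedure or unplanned, using the visit reason and details that they already record. Keep elective procedures as a separate class, since some may follow a rise in AF burden.

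**SAP section 7.9.1.** Keep the all-visit primary label. Prespecify, before the test set is used, that:
- AUROC, sensitivity and PPV with bootstrap intervals are reported for all visits and separately by class, on the same test set;
- the negatives are the same for every class, and a rule covers windows that contain more than one class;
- any conclusion about increased or preventable utilization rests on the unplanned-visit result.

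**Planning and interim analysis.** State which HCU definition lies behind the 21%. At the interim analysis (SAP section 7.8), count the unplanned events and compare them with the plan's minimum.

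**Cost.** One more form field, an addendum and SAP wording change, and classification of HCUs already confirmed. Intervals for the unplanned class will be wider: if the 525 AF-related events at 50% completeness cover all visits, the 320 minimum is met only when at least 61% are unplanned. If the count falls short, the class-specific results can still be reported, with their imprecision shown.

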9.10 Patient Access to Device Data

Select data collected by the market-released LINQ devices will be accessible to patients through Medtronic's research app. Through the app, patients will be able to see and interact with infographic screens and charts that show their average daily, weekly or monthly Atrial fibrillation burden.

Patients will be notified through the app that they should not make any changes in behavior, modifications to treatment, or any other actions related to their health without first speaking with their physician. Patients will be notified that the Medtronic research app does not communicate with other

Version 4.0 (29JUL2022)

Page 31 of 48

Medtronic apps and that data shared through the research app is not shared with their physician and will not be sent back through the CareLink network. Patients will also be notified how the data they are viewing is generated and any reason for delays in their data updates.

